Efficacy and safety of hytrombopag ethanolamine tablets
in the treatment of thrombocytopenia in patients
scheduled for elective surgery

Drug Name: Hytrombopag Ethanolamine Tablets

Principal Investigator: [name]

Leading site: Chengdu City Third People's Hospital

Version Number: 3.1

Version Date: 30 December 2023

protocol summary

study title	Efficacy and safety of hytrombopag ethanolamine tablets in the treatment of thrombocytopenia in patients scheduled for elective surgery
protocol	3.1
version No.	
protocol	December 30, 2023
version date	
Type of clinical study	Non-registration clinical trials
Clinical Study Registry	Investigator-Initiated Trial (IIT)
Clinical Research Unit	Chengdu City Third People's Hospital
study drug	Hytrombopag Ethanolamine Tablets
subject population	Patients with immune thrombocytopenia scheduled for elective surgery
research purposes	To observe the efficacy and safety of hytrombopag ethanolamine tablets in the treatment of thrombocytopenia in patients scheduled for elective surgery
study design	This is an investigator-initiated, single-arm, prospective clinical study to evaluate the efficacy and safety of hytrombopag in the treatment of thrombocytopenia occurring prior to scheduled surgery. ⁹ After signing the informed consent form, the patients will enter the screening period (up to 7 days) and receive oral treatment with hytrombopag after screening. The specific dosage regimen is: 7.5 mg, once daily, orally before bed on an empty stomach, lasting for up to 14 days, PLT \geq 100 \times 10 ⁹ /L. During oral

	administration of hytrombopag, when $PLT \geq 200 \times 10^9/L$, the administration was suspended, and the hemogram was monitored weekly until $PLT < 100 \times 10^9/L$. During the treatment period, blood routine was monitored once every 7 days, $PLT \leq 30 \times 10^9/L$ or $\geq 300 \times 10^9/L$. Patients will have an end-of-treatment visit within 7 days of treatment discontinuation, followed by a 30-day safety follow-up period.
study endpoints	
primary study endpoint:
 
Proportion of patients achieving perioperative platelet count goals ($\geq 80 \times 10^9 \mu g/L$ for major surgery and $\geq 50 \times 10^9 \mu g/L$ for minor surgery) without rescue therapy
 
Secondary endpoints:
 
 1. Median time to platelet count target; 2. Subject platelet count $\geq 50 \times 10^9/L$ maximum duration; 3. Subject platelet count $\geq 80 \times 10^9/L$ maximum duration; 4. Proportion of patients with surgical delay due to thrombocytopenia; 5. Proportion of patients undergoing surgery on schedule; 6. Incidence and severity of bleeding in patients; 7. Proportion of patients receiving emergency treatment; 8. Safety: Adverse events (AEs): include type, incidence, severity, duration, and relationship to study drug.
enrollment criteria (All must comply)	
 1. Subjects ≥ 18 years of age, regardless of gender; definite diagnosis of immune thrombocytopenia. 2. Platelet $\leq 75 \times 10^9/L$ prior to scheduled elective surgery⁹, Surgery is defined by the treating surgeon and hematologist as major or minor surgery based on the duration and complexity of the procedure and the patient's risk of bleeding. 3. Voluntary participation in clinical research and signing of informed consent form.
exclusion	
 1. History of allergy to TPO-RA drugs;

criteria (Excluded if one of them is met)	
2. Severe bleeding symptoms, such as upper gastrointestinal bleeding, bleeding of important organs, intracranial hemorrhage, etc.;
 
3. thrombotic diseases such as pulmonary embolism, arterial thrombosis and disseminated intravascular coagulation (DIC);
 
4. Anti-human immunodeficiency virus antibody or anti-Treponema pallidum specific antibody positive;
 
5. Congestive heart failure New York Heart Association (NYHA) class 3 or 4;
 
6. History of angina pectoris, myocardial infarction or cerebral infarction within 6 months prior to screening;
 
7. Active infections that are difficult to control;
 
8. Pregnant or lactating women;
 
9. Other circumstances judged by the investigator to be unsuitable for inclusion in the study

Study Early Termination Criteria	
1. Death;
 
2. Unanticipated and unacceptable adverse drug reactions occur;
 
3. Withdrawal from the study requested by the subject or his/her legal representative;
 
4. Medical or ethical reasons affect the continuation of the study;
 
5. The circumstances in which withdrawal from the study is deemed necessary by the investigator in the best interests of the subject;
 
6. Subject lost to follow-up;
 
7. Serious violations of the protocol (including serious violations of study enrollment conditions);
 
8. Untolerable toxicity occurred during the study and could not be recovered after dose adjustment;
 
9. Other circumstances necessitating withdrawal from the study in the opinion of the investigator.

Sample Size Estimation and Data	The study was designed as a single-arm exploratory design. Based on previous relevant data reports, the estimated proportion of patients meeting platelet targets was 65%. Using NCSS PASS 15 (LLC. Kaysville, Utah, USA,

Analysis and Statistical Methods	ncss.com/software/pass) software, the two-sided 95% confidence interval (Clopper-Pearson method) for enrollment of approximately 50 subjects was (50.2%, 77.9%), and the confidence interval width was 27.7%.
---	---

1 Background

1.1 Significance and Necessity of the Study

Perioperative bleeding is a thorny problem in surgical operation, and it is also an important reason for rapid recovery after operation.^[1]Platelet is a blood cell directly involved in clot formation and inflammation regulation, its main function is to participate in the body's coagulation and hemostasis. Thrombocytopenia leads to a greatly increased risk of bleeding and transfusion. Thrombocytopenia is very common in perioperative period,Li^[2]A retrospective study conducted by et al showed that patients with cirrhosis and severe thrombocytopenia (PLT≤50×10⁹ μ g/L) had a

higher incidence of major bleeding events after invasive procedures (4.9% VS 1.6%, P = 0.008). Perioperative thrombocytopenia may increase bleeding risk, prolong hospital stay, lead to organ damage, increase medical costs, and in severe cases, lead to death.^[3, 4] The most important perioperative issue in patients with thrombocytopenia is the risk of bleeding.

Several retrospective studies examined the incidence and prognostic impact of preoperative thrombocytopenia in different surgical settings, analyzing prospectively collected data from the American College of Surgeons National Surgical Quality Improvement Program (NSQIP) database. The largest and most comprehensive of these studies was an analysis of 3884400 adult patients who underwent noncardiac surgery between 2006 and 2016.^[5] The incidence of asymptomatic thrombocytopenia was 8.1% in patients undergoing elective surgery. After propensity matching, perioperative transfusions in all patients with thrombocytopenia. However, unlike a similar analysis that did not perform propensity matching, there was no increase in the incidence of other complications. Odds ratio and 95% CI for receiving red blood cell transfusions for mild thrombocytopenia ($100-149 \times 10^9/L$) patients were 1.2, 1.1-1.2, for moderate thrombocytopenia ($75-99 \times 10^9/L$) patients were 1.4, 1.3-1.5, for severe thrombocytopenia ($50-74 \times 10^9/L$) patients were 1.5, 1.2 -1.7 and severe thrombocytopenia ($<50 \times 10^9/L$) Odds ratios and 95% CIs for mortality ranged from 1.2, 1.1 - 1.3 for mild thrombocytopenia, 1.6, 1.3 - 1.8 for moderate thrombocytopenia, 1.6, 1.2 - 2.1 for severe thrombocytopenia, and 1.9, 1.4 - 2.5 for severe thrombocytopenia.

Thrombocytopenia can be caused by many factors during perioperative period, including patient's disease factors, operation type, cardiopulmonary bypass device, drugs, etc.^{9/L} is associated with an increased risk of bleeding, and current clinical practice recommends using different cut-off values prior to invasive surgery. The minimum platelet count required for different surgical procedures varies. Therefore, it is recommended that platelet counts $>50 \times 10^9/L$ be used prior to major general surgery.^{9/L}, platelet count $>100 \times 10^9/L$ in neurosurgery and posterior eye interventions^{9/L}. At present, there is no official standardized process for clinical management of perioperative thrombocytopenia. In March 2023, Guangdong Province Pharmaceutical

Association issued the Consensus of Medical Experts on Perioperative Thrombocytopenia Management.^[6]The principle of treatment is to remove or control the predisposing factors and primary diseases of thrombocytopenia as soon as possible, and give symptomatic treatment if necessary according to the perioperative platelet count requirements. Patients with thrombocytopenia are recommended to control their platelets above the reference threshold of the operation or operation performed to reduce the risk of bleeding during the operation and ensure the smooth operation.

The optimal drug regimen for increasing platelet count in perioperative patients preparing for invasive procedures should take into account the patient's underlying disease. The patient's underlying disease is an immune disease such as ITP, and corticosteroids or immunoglobulin may be given first.^[7]Recombinant human thrombopoietin (rh-TPO), TPO receptor agonist (TPO-RA), etc. can be used to treat thrombocytopenia associated with liver disease.^[8]At present, there are not many drug-related studies on perioperative platelet count increase, and TPO-RA has more evidence-based evidence, among which avatrombopag is also the only one approved by China National Drug Administration. The National Medical Products Administration (NMPA) approves platelet-raising drugs for patients with thrombocytopenia associated with chronic liver disease who are scheduled for diagnostic procedures or surgery. Immunoglobulins can be used when rapid platelet elevation is needed, such as emergency surgery, especially in patients before pregnancy or delivery.

1.2 research status at home and abroad

In Lancet Hematology, Donald et al.^[9]Two methods, intravenous immunoglobulin and eltrombopag, were compared to achieve perioperative platelet count goals By intention-to-treat analysis, 30 of 38 patients (79%) treated with eltrombopag and 22 of 36 patients (61%) treated with intravenous immunoglobulin met perioperative platelet targets (absolute risk difference 17.8%, 95% CI lower bound 0.4%; noninferiority =0.005).

Hani et al.^[10]A single-center, retrospective study of perioperative thrombopoietin receptor agonist romistine in patients with thrombocytopenia was conducted. Patient

characteristics, patient use, procedure, and safety outcomes were collected and analyzed (bleeding, thrombosis, transfusion). 47 patients underwent 51 surgical procedures. Causes of thrombocytopenia include immune thrombocytopenia, chronic liver disease, hematologic malignancies, drug-related thrombocytopenia, and hereditary thrombocytopenia. Median (range) platelet count improved. From $47 \times 10^9 \mu \text{ g/L}$ (9-120 $\times 10^9 \mu \text{ g/L}$) to $164 \times 10^9 \mu \text{ g/L}$ (28-603 $\times 10^9 \mu \text{ g/L}$) at the time of surgery ($P < 0.0001$). Twice-weekly doses of 3 $\mu\text{g/kg}$ increased platelet counts to $> 100 \times 10^9 \mu \text{ g/L}$ within 14 days in 79% of patients. In 96% of cases, surgery was performed as scheduled without delay or cancellation.

Thrombopoietin receptor agonist (TPO-RA) activates tyrosine kinase/signal transducer and activator of transcription (JAK/STAT) by acting on the transmembrane domain of human TPO receptor, induces megakaryocyte survival, proliferation and differentiation, stimulates platelet production, and is not resistant to drug resistance.

As a novel oral thrombopoietin receptor agonist, hytrombopag has been structurally optimized to achieve synergistic and attenuated therapeutic effects, especially in terms of safety, and its effect on bilirubin metabolism is superior to eltrombopag. In a clinical trial to explore the efficacy and safety of hytrombopag in ITP patients, 424 patients were enrolled in a 4:4:1: 1Randomization to treatment with 2.5 mg or 5mg of Hatrombopag and two dose-matched placebo groups. A 10-week double-blind treatment phase followed by a 14-week open-label extension phase. The primary endpoint was platelet response ($\text{PLT} \geq 50 \times 10^9$) at 8 weeks of treatment.⁹ Results After 8 weeks of treatment, 58.9% and 64.3% of patients in the 2.5 mg and 5mg groups achieved platelet response, respectively, which was much higher than that in the placebo group (5.9%).

Based on the above results, we intend to conduct a study on the efficacy and safety of hytrombopag in the treatment of patients with preoperative thrombocytopenia.

[figure not shown]
1.2 Investigational Product Description

1.2.1 Drug name, molecular structure and pharmaceutical properties

Generic Name: Hytrombopag Ethanolamine Tablets

Chemical name: (Z)-5-(2-hydroxy-3-(2-(3-methyl-5-oxo-1-(5,6,7,8-tetrahydronaphthalen-2-yl)-1H-pyrazole-4 (5H)-ylidene) hydrazino) phenyl) furan-2-carboxylic acid ethanolamine salt (1:2)

Chemical formula:

Molecular Formula: C₂₅H₂₂N₄O₅ · 2C₂H₇NO

Molecular weight: 580.64

Appearance: This product is a film-coated tablet, light brown to brown after removing the coating

Formulation: Tablet

Strength: 2.5 mg

Route of Administration: Oral

1.2.2 Nonclinical pharmacology studies

In vitro studies showed that hytrombopag ethanolamine significantly promoted the proliferation of thrombopoietin (TPO) receptor positive cell line 32D-MPL with EC₅₀ of 0.4 nM, which was significantly stronger than that of eltrombopag (about 34 times), and also significantly promoted the proliferation and differentiation of human umbilical cord blood CD34 + cells in vitro with EC₅₀ of 2.3 nM and 4.5 nM, which were

significantly stronger than that of eltrombopag.(about 38 and 20 times); In the experiments of promoting cell cycle, resisting apoptosis and activating TPO receptor-dependent STAT and MAPK signal transduction pathways, the activity of hytrombopag ethanolamine was stronger than that of eltrombopag. By using the hollow fiber evaluation model established in nude mice, it was found that hytrombopag ethanolamine was effective (the drug effect lasted for 3 days), and it specifically promoted the proliferation of 32D-MPL cells in vivo and the activation of downstream STAT/MAPK signal transduction pathway. In addition, M1, a metabolite of hytrombopag ethanolamine, promoted the proliferation of 32D-MPL cells and the activation of STAT/MAPK signal in a dose-dependent manner, but its activity was significantly weaker than that of hytrombopag ethanolamine.

1.2.3 pharmacokinetic study

The pharmacokinetics of hytrombopag administered orally to healthy subjects and patients with chronic ITP for 10 consecutive days at doses ranging from 2.5 mg to 7.5 mg were evaluated. The results were similar to those of single-dose trials. The plasma concentration-time curve showed a double-peak phenomenon, i.e., the first peak occurred at 1-2 h after administration, indicating a rapid absorption process, and the second peak occurred at 7-10 h after administration.(Zheng et al., 2017). After oral administration of 2.5~7.5 mg of hitrombopag in patients with chronic ITP on an empty stomach, the plasma concentration increased with the increase of dose. Once daily, the plasma concentration reached its peak at 2-5 h after administration, and the plasma concentration reached steady state on about the 10th day after continuous administration. After absorption, hitrombopag was extensively metabolized, and the main excretion route was feces. The elimination half-life of hatrombopag in plasma was estimated to be 11.9- 40.1 h.

1.2.4 pharmacodynamic studies

After 10 consecutive days of oral administration of 2.5-7.5 mg dose range of

hetrombopag to healthy subjects, platelet count (PLT) showed a continuous increase from the sixth day of continuous administration, and reached the peak at about 12~14 days (2~4 days after discontinuation). The average maximum increase percentage of PLT compared with baseline in 2.5 mg, 5 mg and 7.5 mg groups was 34.1%, 69.9% and 98.2%, respectively. PLT basically returned to baseline in the 2.5 mg group on D28 after drug withdrawal, while platelet growth remained 18.8% and 32.2% in the 5 mg and 7.5 mg groups. Patients with chronic ITP received oral doses ranging from 2.5 mg to 7.5 mg for 14 consecutive days. The results showed that $PLT \geq 50 \times 10^9 / L$ in 12.5%, 58.3% and 66.7% of patients in the 2.5 mg, 5 mg and 7.5 mg groups, respectively, on D28 (14 days after drug withdrawal).⁹

1.2.5 clinical efficacy studies

1.2.5.1 A Phase III Clinical Study of Hytrombopag in Primary Immune Thrombocytopenia

In a multicenter, randomized phase III clinical study of hetrombopag in primary immune thrombocytopenia, 424 patients ($PLT < 30 \times 10^9 / L$ at 48 hours prior to enrollment) with at least 6 months of history of primary ITP who had failed or relapsed to at least one line of ITP therapy⁹ After 10 weeks of treatment, the patients entered the 14-week open-label phase. The treatment group continued to receive the dose adjusted in the previous phase, while the placebo group received the positive control drug eltrombopag (initial dose 25 mg/d) and maintained $PLT(50-150) \times 10^9 / L$. The results showed that after 8 weeks of treatment, hetrombopag achieved therapeutic response ($PLT \geq 50 \times 10^9 / L$) was significantly higher than placebo (Hytrombopag 2.5 mg vs. Hytrombopag 5 mg vs. placebo: 58.9% vs. 64.3% vs. 5.9%, $P < 0.0001$), and the onset of action was rapid, with a median of 21 days for the 2.5 mg group, respectively (95CI: 15-25), 5mg group 14 days (95%CI: 8-14). 24 weeks of treatment with hitrombopag produced a sustained platelet response, with 44.8% of subjects having platelet counts $\geq 50 \times 10^9 / L$ times greater than 75% of total detection times, platelet count $\geq 50 \times 10^9 / L$ The median (minimum, maximum) maximum duration of/L was 64(6,168) days and the median total duration

was 103(6,168) days.

1.2.5.2 A Phase II Clinical Study of Hytrombopag in Severe Aplastic Anemia with Poor Response to IST

In a multicenter, single-arm, open-label phase II study of severe aplastic anemia with poor response to IST, 55 SAA patients who had a poor response to IST and were not transplant candidates/unwilling received hetrombopag at a starting dose of 7.5 mg.⁹ The results showed that 23 patients (41.8%) achieved hematological response at week 18 and 24 patients (43.6%) achieved hematological response at week 24. For those patients who achieved hematologic response during the study, the median remission time was not reached due to the small number of relapses, and the relapse-free survival rates at 9 and 12 months were 82.2%(95% CI: 62.2%, 92.2%).

2 Purpose of the study

To observe the efficacy and safety of hytrombopag ethanolamine tablets in the treatment of thrombocytopenia in patients undergoing elective surgery.

3 Study endpoints

3.1 primary study endpoint

Proportion of patients achieving perioperative platelet count goals ($\geq 80 \times 10^9 \mu \text{g/L}$ for major surgery and $\geq 50 \times 10^9 \mu \text{g/L}$ for minor surgery) without rescue therapy

3.2 secondary study endpoints

- 1)Median time to platelet count target;
- 2)Subject platelet count $\geq 50 \times 10^9 \text{L}$ maximum duration;

- 3)Subject platelet count $\geq 80 \times 10^9/L$ maximum duration;
- 4)Proportion of patients with surgical delay due to thrombocytopenia;
- 5)Proportion of patients undergoing surgery on schedule;
- 6)Incidence and severity of bleeding in patients;
- 7)Proportion of patients receiving emergency treatment;
- 8)Safety: Adverse events (AEs): include type, incidence, severity, duration, and relationship to study drug.

4 Experimental design

This is an investigator-initiated, single-arm, prospective clinical study to evaluate the efficacy and safety of hytrombopag in the treatment of thrombocytopenia occurring prior to scheduled surgery.⁹After signing the informed consent form, the patients will enter the screening period (up to 7 days) and receive oral treatment with hytrombopag after screening. The specific dosage regimen is: 7.5 mg, once daily, orally before bed on an empty stomach, lasting for up to 14 days, $PLT \geq 100 \times 10^9/L$. During oral administration of hytrombopag, when $PLT \geq 200 \times 10^9/L$, the administration was suspended and the hemogram was monitored every 7 days until $PLT < 100 \times 10^9/L$. During the treatment period, blood routine was monitored once every 3 days, $PLT \leq 30 \times 10^9/L$ or $\geq 300 \times 10^9/L$. Patients will have an end-of-treatment visit within 7 days of treatment discontinuation, followed by a 30-day safety follow-up period.

5 Management of Subjects

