5.2 Exclusion criteria (one of which is excluded)

- 1) History of allergy to TPO-RA drugs;
- 2) Severe bleeding symptoms, such as upper gastrointestinal bleeding, bleeding of important organs, intracranial hemorrhage, etc.;
- 3) thrombotic diseases such as pulmonary embolism, arterial thrombosis and disseminated intravascular coagulation (DIC);
- 4) Anti-human immunodeficiency virus antibody or anti-Treponema pallidum specific antibody positive;
- 5) Congestive heart failure New York Heart Association (NYHA) class 3 or 4;
- 6) History of angina pectoris, myocardial infarction or cerebral infarction within 6 months prior to screening;
- 7) Active infections that are difficult to control;
- 8) Pregnant or lactating women;
- 9) Other circumstances deemed unsuitable for inclusion in the study by the investigator.

6 Dosing Regimen

Subjects must take the drug on an empty stomach every morning (overnight fasting for at least 8 hours), breakfast must not be eaten for 2 hours after dosing, and subjects are required to take all trial drugs of the day once a day, swallow the trial drugs whole, and do not chew, divide or crush them.

7. Concomitant Medications/Concomitant Therapy

The investigator has the right to decide at any time whether to give the following supportive treatment to the subject: transfusion supportive treatment (such as red blood cells and platelets). During this trial, except for the basic treatment and drugs used for

treatment or prevention of adverse events that have been taken stably before the trial, any other drugs are prohibited in principle. Any drugs used during the trial other than the trial drugs should be recorded in detail in the eCRF, and the records should include: drug name, dose, date of administration and indication for use.

8 Test observation methods

During the treatment period, blood routine was monitored once every 7 days, $PLT \leq 50 \times 10^9/L$ or $\geq 300 \times 10^9/L$. Patients will have an end-of-treatment visit within 7 days of treatment discontinuation, followed by a 30-day safety follow-up period.

9 Adverse events and evaluations

9.1 adverse event definitions

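### Version 3.1 gives incompatible instructions on blood-count interval (3 or 7 days) and dosing time (bedtime or morning), apparently also on the low-count value (30 or 50), and does not say which section governs

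*Protocol*

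**What the plan says.** Three places in the protocol set the on-treatment blood-count schedule, each with a low-count value in the same sentence:

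- Synopsis, study design: "blood routine was monitored once every 7 days, $PLT \leq 30 \times 10^9/L"
- Section 4, Experimental design: "During the treatment period, blood routine was monitored once every 3 days", with the low-count value following directly: "once every 3 days, $PLT \leq 30 \times 10^9/L"
- Section 8, Test observation methods: "During the treatment period, blood routine was monitored once every 7 days, $PLT \leq 50 \times 10^9/L"

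Three places set or describe the time of dosing:

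- Synopsis and Section 4, in the same words: "7.5 mg, once daily, orally before bed on an empty stomach"
- Section 6, Dosing Regimen: "Subjects must take the drug on an empty stomach every morning (overnight fasting for at least 8 hours". Section 6 also bars breakfast for 2 hours after the dose.

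Two further rules bear on the count schedule. If PLT reaches 200 × 10⁹/L, Section 4 says "the administration was suspended and the hemogram was monitored every 7 days until" the count falls below 100. At the end of dosing, "Patients will have an end-of-treatment visit within 7 days of treatment discontinuation".

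**The concern.** A single daily dose cannot be taken both at bedtime and in the morning after an overnight fast, and routine counts cannot be both 3 and 7 days apart. These are conflicts in the current text of version 3.1. They are also protocol content: a statistical analysis plan does not tell a patient when to take a tablet or a nurse when to draw blood.

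The stake for the analysis lies in secondary endpoints 1 to 3: median time to platelet target, and maximum duration at ≥50 and at ≥80. These are seen only when blood is drawn. If staff follow different sections, patients are timed with different resolution, and a report could not say which schedule the protocol required. The stake for conduct is that the count interval also limits how soon a platelet count of 200 or more is noticed, which is the trigger for suspending the drug.

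**Working it through.** **1. The passages side by side**

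| Item | Synopsis | Section 4 | Section 6 | Section 8 |
|---|---|---|---|---|
| Count interval | 7 days | 3 days | – | 7 days |
| Low-count value (× 10⁹/L) | ≤30 | ≤30 | – | ≤50 |
| High-count value (× 10⁹/L) | ≥300 | ≥300 | – | ≥300 |
| Dosing time | bedtime | bedtime | morning | – |

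The odd one out is Section 4 for the interval, Section 8 for the low-count value and Section 6 for dosing time. No one section can therefore be treated as the reliable text. Nothing in the protocol says which prevails.

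**2. Can another rule reconcile the interval?** The 7-day count after suspension at PLT ≥200 is a separate instruction for patients whose drug is on hold. The conflicting sentences all concern routine counts during treatment, so it does not reconcile them.

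**3. Number of scheduled counts.** Inputs: a course of up to 14 days (synopsis, Section 4) and intervals of 3 or 7 days. Scheduled counts = whole intervals in the course.
- Every 3 days: 14/3 = 4.67, so 4 counts.
- Every 7 days: 14/7 = 2 counts.

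**4. Delay in recording a crossing.** With counts every *k* days, a crossing just after one count is first seen at the next, up to *k* days later: up to 3 days or up to 7 days. This is a worst case, not a ranking for every patient. Counting from the first dose, a crossing between days 6 and 7 is seen on day 7 on the weekly schedule and on day 9 on the 3-day schedule. The recorded start of an episode at ≥50 or ≥80 carries the same uncertainty, so maximum duration is affected too.

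**5. PLT ≥200.** In a patient who crosses 200, dosing may continue up to 3 or up to 7 days before the crossing is seen. How many would cross is not known. As an indication only, Section 1.2.4 gives a mean maximum rise of 98.2% at 7.5 mg in healthy subjects. From the highest eligible baseline, 75 × 1.982 = 148.65, about 149. Reaching 200 from 75 needs 200/75 − 1 = 166.7%.

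**6. Sample size.** The interval in Section 10.4 reproduces. Clopper-Pearson limits are the 2.5% quantile of Beta(x, n − x + 1) and the 97.5% quantile of Beta(x + 1, n − x). With n = 50 and x = 0.65 × 50 = 32.5 they are 50.2% and 77.9%, width 27.7%. Nothing in this point changes it.

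**The case against.** The best reply is that these are drafting slips with an obvious majority reading. Two of the three places agree on each item, no effect on the primary endpoint is shown, and other counts may fill the gaps. Part of this stands. Triggered counts, a preoperative count or the end-of-treatment visit would narrow the difference between the schedules, by an amount the text does not allow one to estimate. But a majority of passages is not a rule of precedence, and the dissenting place on dosing is the section devoted to dosing, where staff would look first.

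The low-count value deserves more caution. The two figures differ in print and stand in parallel sentences, but the action attached to them is not readable in the extracted text. It is therefore not proven that 30 and 50 trigger the same thing, and the missing action is not itself a fault of the plan.

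A reader might go further and infer that the recorded median time to target would shift by a definite number of days, or that the 3-day schedule misses the platelet peak and needs an extra count on day 14. The documents do not support this:

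- The peak at about 12 to 14 days in Section 1.2.4 was seen in healthy subjects after 10 days of dosing, 2 to 4 days after stopping.
- The protocol does not fix how days are numbered. If days are counted from the first dose, the 14th daily dose falls on day 13, and a day-14 count comes after it.
- Time to target is not limited to counts on treatment.

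Nor does the text support an inference that the drug would commonly be continued above 200: the indicative figure of about 149 suggests such crossings would not be typical.

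**Conclusion.** The point holds. The contradictions on count interval and dosing time are certain from the text, and the one on the low-count value is apparent. The protocol cannot be followed as written.

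The size is about four against two scheduled counts in a 14-day course, and a worst-case recording delay of 3 against 7 days for secondary endpoints 1 to 3. The same bounds apply to noticing PLT ≥200 in any patient who gets there. No endpoint effect is quantified for dosing time or the low-count value. A reader might infer bias in the primary endpoint; the documents do not show one, because that endpoint rests on reaching a perioperative target, which implies a count near surgery.

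These figures assume a full 14-day course and scheduled counts only. The dosing sentence also contains a PLT ≥100 clause whose role is not readable. If it stops treatment early, fewer on-treatment counts would be scheduled on either interval. This should be corrected, but it does not undermine the trial's main result.

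**What to change.** Amend the synopsis and Sections 4, 6 and 8 so that they state, in identical words, one count interval, one low-count value and one dosing time with a fasting rule that fits it. The choice is the investigators':

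- **Interval.** If weekly counts are intended, correct Section 4. If 3-day counts are intended, correct the synopsis and Section 8.
- **Dosing time.** If bedtime is intended, replace the morning and breakfast rule in Section 6 with a bedtime fasting window. If morning is intended, correct the synopsis and Section 4.
- **Low-count value.** Print one figure in all three places.

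The cost is amendment wording and a clarification to staff. Section 11.2 requires agreement among the investigators, and ethics approval if the revision newly affects subject safety or requires a change to the consent form. Weekly counts add no draws to the synopsis and Section 8 schedule. Counts every 3 days mean about two more draws per patient than weekly, (4 − 2) × 50 = about 100 for 50 patients, in return for finer timing.
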